12.2 Endothelial function

Endo-PAT 2000 (Itamar Medical Ltd., Caesarea, Israel) will be used to measure endothelium-dependent vaso-reactivity as previously described¹⁸. In brief, before measurements, the subjects will be in supine position for a minimum of 10 minutes, in a quiet, temperature-controlled room with dimmed lights.

Probes will be placed on both index fingers and pulse wave amplitudes will be detected and recorded during the study. After a five-minute baseline measurement, arterial flow will be occluded using a cuff on the non-dominant arm. The cuff will be inflated to 60 mmHg above systolic pressure. After five minutes of occlusion, the cuff will be rapidly deflated to allow reactive hyperemia. Pulse wave amplitudes will be recorded again for at least five minutes. The ratio of the peripheral arterial tone (PAT) signal after cuff release compared with baseline will be calculated through a computer algorithm automatically normalizing for baseline signal and indexed to the contra lateral arm. The calculated ratio represents the reactive hyperemia index (RHI) ¹⁹.

12.3 Bone densitometry and body composition

Bone density scanning, also called dual-energy x-ray absorptiometry (DXA) or bone densitometry, is an enhanced form of x-ray technology that is used to measure bone loss. DXA measurement will be performed with a GE Lunar iDEXA (GE Healthcare, Waukesha, WI, US) full size for the purpose of estimating percentage body fat according to the departmental Standard Operating Procedure. Body regions are defined using standard anatomical partitions. Scan areas are analysed to determine lean mass, fat mass, bone mineral content, and total body composition.

12.4 Laboratory measurements (Clinical and hormonal)

Insulin and c-peptide will be measured by chemiluminescence on an ADVIA Centaur system (Siemens Healthcare Diagnostics, Eschborn, Germany). Fertility hormones (AMH (Anti-muellerian hormone), testosterone, cortisol, thyreotropin, triiodothyronine and thyroxine, estrogen, SHBG (sexual hormone binding globulin), LH (luteotropic hormone), FSH (follicle stimulating hormone) and 25(OH)vitamin D will be measured using automated analyzers: AMH by Beckmann-Coulter, Krefeld, Germany; testosterone, cortisol, thyreotropin, triiodothyronine and thyroxine by Siemens ADVIA Centaur, Eschborn, Germany; SHBG by Roche Diagnostics, Mannheim, Germany; estrogen, LH and FSH by Triturus, Biomedical Diagnostics, Antwerp, Belgium, 25(OH)vitamin D by iSYS, IDS, Boldon, U.K.) respectively. Samples for appetite hormones (Leptin, Ghrelin, PYY, and others) will be stored at -80°C until analysis after centrifugation. In addition, lactose intolerance (as defined by the locus LCT-13910) and vitamin D genotypes will be determined by standardized PCR from EDTA blood samples. FFA will be measured enzymatically (Wako Chemical, Neuss, Germany) on an Olympus AU640 (Olympus Diagnostica, Hamburg, Germany). Routine parameters will be determined using a cobas[®] analyzer (Roche Diagnostics, Mannheim, Germany).

12.5 Laboratory measurements (Specialized Research – Aging Parameters)

Molecular parameters of aging will be measured by a variety of already established methods at the [name] laboratory at the Institute of Molecular Biosciences, University of Graz. Levels of different cell signaling and cell cycle proteins (p16, p21, p53, NCX, mTOR, Ras, Rb) will be measured using capillary-based western blot system – Wes™ (Proteinsimple, San Jose, California, USA). Inflammatory markers, insulin signaling, as well as precise characteristics of molecular pathways will be analyzed using certified and commercially available V-PLEX Assays (Meso Scale Discovery, Rockville, Maryland, USA). Epigenetic changes (methylation and acetylation) will be analyzed via traditional western blotting. All methods based on antigen-antibody interaction will be done using commercially available antibodies, in order to assure better reproduction and optimal processes and procedures. Different “omics” (metabolomics, proteomics, acetylproteomics) as well as levels of different polyamines will be measured using HPLC-coupled mass spectrometry (MS) or HPLC-coupled MS/MS methods. Different parameters of cell death (apoptosis, stress resistance, mitochondrial damage) and damage caused by aging (telomere length, double strand breaks, chromosomal aberrations, heterochromatin changes) will be analyzed using flow cytometry systems BD Bioscience LSRFortessa and FACSARIA IIu at the NAWI Graz Central Lab “Graz Cell Informatics and Analyses”. The telomerase activity will be measured by Human Telomerase Reverse Transcriptase (hTERT) ELISA Quantitation Kit (GenWay, San Diego, California, USA).

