8.2 Secondary outcome measures in the cohort study

- Levels of different cell signaling and cell cycle proteins (p16, p21, p53, NCX, mTOR,

Ras, Rb)

- Differences in parameters of cell death (apoptosis, stress resistance, mitochondrial damage) between groups
- Differences in telomere length, double strand breaks, chromosomal aberrations, heterochromatin between groups
- Differences in telomerase activity between groups
- Differences in endocrine parameters of fertility and nutritional regulation

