Data on the effects of ADF on metabolic parameters, human physiology, aging process and molecular cellular processes in healthy subjects is very limited and a therefore an accurate sample size estimation impossible. However, we reviewed available data and used data on insulin sensitivity from a similar, albeit not entirely comparable study population with a HOMA-IR of 3 ± 1.1 (mean \pm SD)⁷. Assuming a power of 80% and a type I error rate of 5%, we would need 50 subjects per group to demonstrate an effect size of 15%, which has been demonstrated previously³⁸. Therefore the sample size of 50 subjects in the ADF and 50 subjects in the control group, as chosen for our cohort study, seems to be reasonable. In addition, previous publications have also suggested a sample size of 50 subjects per group for such types of studies with insufficient details about the outcome parameters required for a sample size estimation³⁹. Subjects in the control group will be asked to participate in a pilot, randomized controlled trial, where they are randomized to either ADF or continuing in the control group. We expect an acceptance rate of about 40%, hence a sample size of about 10 participants per group.

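### Telomerase activity is a named secondary outcome in both study parts, but the only assay assigned to it appears, from its name, to measure the amount of hTERT protein

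*Protocol*

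**What the plan says.** Protocol section 8.2 lists among the cohort study's secondary outcomes "Differences in telomerase activity between groups". Section 8.4 repeats the same line for the randomised trial.

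The method is in section 12.5, which covers the aging parameters: "The telomerase activity will be measured by Human Telomerase Reverse Transcriptase (hTERT) ELISA Quantitation Kit". The manufacturer is named. The read-out, its units and the cells or fluid to be assayed are not.

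Two other statements bear on how to read this. Section 8.2 describes a different group of proteins by amount: "Levels of different cell signaling and cell cycle proteins". Section 12.5 also says of the class of method to which an ELISA belongs: "All methods based on antigen-antibody interaction will be done using commercially available antibodies".

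**The concern.** The outcome is a function of an enzyme. The assay, by its name, quantifies one protein component of that enzyme. These are different quantities, and the protocol does not say how one is to stand for the other.

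If the protocol is followed as written, the results table would carry a row called telomerase activity whose entries are amounts of hTERT. Two misreadings could follow. A difference between the fasting and control groups could be taken as a change in enzyme activity when only the amount of protein differs. A finding of no difference could be taken as evidence that fasting leaves telomerase activity unchanged, although activity was not measured.

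This is not a detail that a statistical analysis plan would normally supply. The protocol fixes both the outcome and the assay, and no analysis can turn a protein amount into an enzymatic activity.

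**Working it through.** No arithmetic applies, and the protocol gives no figure for this outcome to reproduce. The check sets the outcome definition beside the assay and then looks for anything in the protocol that would bridge the two.

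1. **What is the outcome?** Activity, in both 8.2 and 8.4. The word does not look accidental. Both lists describe another group of proteins (p16, p21, p53 and others) as levels, so the protocol distinguishes amount from activity and uses activity for telomerase.

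2. **What does the assay deliver?** The kit's name states the analyte (hTERT), the technique (ELISA) and the operation (quantitation). An ELISA detects antigen by antibody binding, and its usual result is a concentration of that antigen. On that general principle the kit returns an amount of hTERT. It would not show whether the enzyme extends telomeric DNA. This step is inferred from the name.

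3. **Does another method fill the gap?** The methods in section 12.5 are assigned as follows:

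| Method in 12.5 | Assigned to |
|---|---|
| Capillary western blot | Cell signalling and cell cycle proteins |
| V-PLEX assays | Inflammatory markers, insulin signalling, molecular pathways |
| Traditional western blot | Epigenetic changes |
| HPLC-coupled mass spectrometry | Omics, polyamines |
| Flow cytometry | Cell death; damage from aging, including telomere length |
| hTERT ELISA | Telomerase activity |

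   Only the last row concerns telomerase. No functional telomerase assay appears elsewhere in section 12.

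4. **Does the protocol justify a proxy?** No. It does not describe hTERT concentration as a surrogate for activity, and it gives no conversion or validation. Section 12.5 says plainly that activity is what will be measured.

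5. **How far does the problem reach?** Telomerase activity is one of five secondary bullets in 8.2 and one of four in 8.4. Section 12.26 declares the analyses of primary and secondary outcomes descriptive and exploratory. Its sample size argument rests on HOMA-IR (the authors "used data on insulin sensitivity from a similar, albeit not entirely comparable study population"), not on telomerase. Section 8.1 and the readable items of 8.3 contain no telomerase measure. The mismatch therefore stays within this one outcome.

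**The case against.** The strongest reply has four parts.

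*The read-out is not documented.* The protocol gives a kit name and a manufacturer, and nothing on units, antibody specificity or sample material. This stands, and the finding has to carry it as an assumption. A reader might go further and infer that the kit is known to count inactive as well as active protein. The documents do not support that, because it depends on antibodies they do not describe. The point does not need it: an amount and an activity differ whichever forms of the protein are bound.

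*The protocol states its operational definition openly.* Section 12.5 tells the reader how activity will be obtained, and the kit's own name identifies hTERT as the reverse transcriptase, so this could be a loosely named proxy. That is a fair defence of collecting the data but not of the label. A proxy has to be called one, and a reader of the results would see only the outcome name.

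*The objective survives.* A reader might infer that the mismatch undermines the secondary objective on aging markers. It does not. Section 7.2 speaks of molecular markers and pathways of aging in general and does not name telomerase activity. An hTERT amount can still serve as such a marker, and telomere length is a separate outcome with its own method. This part of the reply stands in full.

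*The analyses are exploratory.* That limits the weight of the point. It does not make it acceptable to report one quantity under the name of another.

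**Conclusion.** The point holds as a mismatch between a named outcome and the assay assigned to it. The protocol promises telomerase activity in both study parts and, on the natural reading of the kit's name, would deliver an amount of hTERT protein.

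The conclusion rests on one assumption: that the kit reports hTERT concentration and gives no functional read-out. The insert could confirm or overturn this. It would be too strong to say that the trial is unable to yield any information on activity, because that treats the inference from the name as established fact.

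The size is modest. Every value of this outcome would be mislabelled, but it is a single exploratory secondary outcome. The change is worth making because it alters what may be claimed from these data at almost no cost.

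**What to change.** First check the kit documentation. If it shows a functional read-out, cite that in section 12.5 and the point is settled.

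Otherwise rename the outcome in sections 8.2 and 8.4, and the matching sentence in 12.5, to *hTERT protein concentration (ELISA)*. Add one sentence to 12.5 stating that no conclusion on telomerase activity will be drawn from it. This needs no new samples, assay or analysis. The only loss is a slightly narrower claim for this outcome.

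If the investigators do want activity itself, renaming will not provide it. They would have to name a functional assay and the sample it needs, which is a larger change than the wording correction proposed here.

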12.6 Physical activity measurement

The MoviSens-device consists of a 5.3×3×2-cm-sized body and can be fixed with a clip to the hip. During the measurements, the sensor will be placed on the right side of the subjects' hip. The sensor is a three-axial acceleration sensor with a range of ±8 g, a resolution of 12 bit and a sampling rate of 128 Hz. The recorded data from the sensor, including raw data from the acceleration sensor, can be displayed on a computer when connected to it via USB cable. Energy expenditure is displayed in steps of 1 s. Short time intervals allow monitoring spontaneous activities. The recognition of different activities is based on the extraction of mathematical and statistical features of the raw acceleration signal. The features are calculated for each segment of 4 s. Calculated features are, amongst others, maximum frequency, step count, and the number of mean crossings. These features are the input information of a decision tree which classifies the activity of the person. Activities that can be detected are rest (combination of lying, sitting, and standing); bicycle or ergometer; going upstairs; walking (combination of jogging, going downstairs, walking slow, normal, and fast); and unknown activity. According to information from the manufacturer, the decision tree was generated using data of approximately 300 subjects who performed

daily life activities. The accuracy of the activity recognition algorithm is discussed by Jatobá et al. ²⁰. According to the detected activity, one of five different models is selected.

12.7 Intima media thickness (IMT)

The measurement of the common carotid artery intima and media combined layers as determined by high-resolution B-mode ultrasonography is widely recognized as a useful tool for early identification for systemic atherosclerosis. Intima media thickness (IMT) and plaque will be measured using high resolution ultrasound. IMT will be measured in the common carotid artery in a segment of 2 cm below the bulb. Near and far wall measurements of both sides will be combined to calculate mean IMT ²¹. Plaque burden will be quantified using the B-score according to the ACAPS protocol ²².

12.8 Food frequency questionnaire (FFQ) and hormonal scores

A self-administered, semi-quantitative FFQ was developed to assess usual food consumption within the German Health Examination Survey for Adults 2008-2011 (DEGS) ²³. The relative validity of this questionnaire was studied among participants of another nationwide survey, the German National Nutrition Monitoring (NEMONIT) ²⁴. The FFQ includes questions about the frequency and the amount of 53 food items, consumed during the past four weeks. Frequency of consumption of food items was asked according to specified categories. In addition, the respondents had to indicate the portion size of the food items consumed in predefined answering categories. Pictures were used to aid the estimation of portion size for 33 food items. In total, 29 food groups will be presented by the food frequency questionnaire. Standardized fertility questionnaires are published medical history questions asking for menarche/menopause, menses regularity and childbirth/child wish in female and complementary data in male probands. Ferriman-Galway Score and Hamilton-Norwood Scheme are standardized questionnaires/schemes for female hirsutism or male baldness, respectively. Probands and/or medical doctors use pictograms for a scoring of female/male body hair.

12.9 Non-invasive 24h ambulatory blood pressure monitoring

Subjects wear the blood pressure device for a single 24-hours period. During this time, the device is programmed to inflate and record blood pressure at pre-specified intervals (usually every 15min during daytime hours and every 30 minutes during night-time hours), which provides approximately 50-75 blood pressure recordings during the 24-hours period. Study participants are asked to keep an activity log throughout the 24-hour period so activities can be mapped onto the blood pressure recordings. The process for educating subjects about the blood pressure device and setting up the test takes

approximately 10 minutes. Patients should undergo testing on a regular workday. They should be educated about the process of monitoring and the importance of maintaining an activity log.

12.10 Resting energy expenditure (REE)

The resting energy expenditure (REE) is a component of energy expenditure that is measured by indirect calorimetry (IC). Subjects must at least 30-minute rest after at least 8 hours of sleep and after at least 3 hour fasting. During measurement, subject must be kept fully awake, lied down quietly, completely relaxed and breathing normally. The measurements took place for at least 30 minutes and were performed in standard neutral hospital room temperature. A breath mask will be placed over the head of the subject. Oxygen consumption and carbon dioxide production will be measured and energy expenditure will be calculated by the Weir formula ²⁵.

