8. OUTCOMES

8.1 Primary outcome measures in the cohort study

- Differences in body composition (fat mass and lean body mass) between groups
- Differences in resting energy expenditure between groups
- Differences in insulin sensitivity (Matsuda Index, ISI, HOMA-Index, QUICKI) between groups
- Difference in glycaemic pattern (continuous glucose measurement) between the two groups
- Differences in endothelial function (Mean Intima media thickness, Reactive Hyperaemia Index, Stiffness Index, Aortic augmentation index) between groups
- Differences in mean 24h blood pressure between groups
- Differences in hormonal regulation (fertility, appetite hormones and others)

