11. STUDY PROCEDURES

11.1 Schedule of study procedures of the cohort study

	Visit 1	Visit 2 (9 ± 4 days after visit 1)
Informed Consent	X	
Inclusion/exclusion criteria	X	
Demography, medical history	X	

Concomitant medication	X	X
Vital signs	X	X
Physical examination	X	
Blood sampling (FMD)	X	X
Dual-energy X-ray absorptiometry (DXA)		X
Oral glucose tolerance test (OGTT)	X	X (ADF group only)
Electrocardiography (ECG)	X	
Questionnaires (FFQ, Physical Activity)		X
Retinal vessels analyser		X
Continuous Glucose monitoring (CGM)	X	
Hand-Grip Test		X
Accelerometer (Movisens®)	X	
Endothelial function (EndoPat 2000)		X
Intima media thickness (IMT)		X
Pulse wave analysis		X
Buccal mucosa sampling	X	
24h blood pressure measurement	X	
Sputum sampling	X	
Faeces sampling	X	
Echocardiography	X	
Resting energy expenditure (REE)		X
Bioelectrical impedance analysis (BIA)		X
Dry eye assessment (optional)		X
Flow mediated dilatation (FMD)		X

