11.2 Visit Schedule for the cohort study

Visit 1

- Sufficient time will be provided and subjects will be encouraged to discuss all queries with the research team
- Informed consent for the study will be obtained by an investigator
- Biobank informed consent will be obtained by an investigator
- Check inclusion and exclusion criteria

- Demographics will be obtained: date of birth, gender, race, smoking status, alcohol consumption
- Weight
- Height
- Waist-Hip Ratio
- Medical history and standardized questionnaire on fertility outcomes
- Concomitant medication
- Vital signs: resting pulse and blood pressure
- Blood sampling
- ECG
- Food Frequency Questionnaire and Ferriman-Galway Score/Hamilton-Norwood Scheme
- Baseline blood tests (fasting): Full blood cell count, renal function tests, liver function tests,
- Pregnancy test in female woman of childbearing age
- Oral glucose tolerance test (OGTT)
- Application of the 24h blood pressure device
- Application of continuous glucose monitoring
- Application of accelerometer (Movisens®)

Visit 2 (9 ± 4 days after visit 1)

- Vital signs, Weight
- Physical examination
- Concomitant medication review
- Resting energy expenditure (REE)
- Measurement of endothelial function (EndoPAT 2000)
- Flow mediated dilatation (FMD)
- Blood sampling
- Oral glucose tolerance test (OGTT)
- IMT measurement
- Retinal vessel analyser
- Hand Grip Test
- Pulse wave analysis
- Echocardiography
- Collection and analysis of 24h blood pressure monitor
- Collection and analysis of accelerometer

- Removal of continuous glucose monitoring
- Dual-energy X-ray absorptiometry (DXA) and hand grip test
- Collection of sputum and faeces samples
- Buccal mucosa sampling
- Informed consent for RCT (healthy control group willing to participate in the RCT)
- Bioelectrical impedance analysis (BIA)
- Dry eye assessment (optional)

Visit 3 (2 weeks before visit 4) → only those subjects participating in the pilot RCT

- Application of continuous glucose monitoring

Visit 4 (4 weeks ± 1 week after visit 2) → only those subjects participating in the pilot RCT

- Vital signs, Weight
- Physical examination
- Concomitant medication review
- Resting energy expenditure (REE)
- Measurement of endothelial function (EndoPAT 2000)
- Flow mediated dilatation (FMD)
- Blood sampling
- Food Frequency Questionnaire
- Oral glucose tolerance test (OGTT)
- Removal of continuous glucose monitoring
- Collection of sputum and faeces samples
- Buccal mucosa sampling

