12. METHODS

12.1 Oral glucose tolerance test (OGTT)

Various insulin sensitivity indices derived from a frequently sampled, extended oral glucose tolerance test (OGTT) will be calculated accounting for the various weighting of hepatic and peripheral insulin sensitivity expressed by the different indices. Insulin, C-peptide and glucose will be measured before and 15, 30, 60 and 120 minutes after ingestion of 75g glucose ([®]Glucoral 75 citron, Germania Pharmazeutika, Vienna). In addition, lipid-parameters (total cholesterol, triglycerides, HDL, LDL, free fatty acids) and a routine safety lab will be measured. The OGTT will be performed after an overnight fast (apart from water). A standard gauge cannula will be placed into a subcutaneous vein for blood sampling. In order to prevent blood clotting in the cannula and to keep the cannula working it will be occasionally flushed with sterile normal saline. A pre-meal blood sample will be taken (-5 mins) and then all subjects will be asked to drink the sugar solution over a period of 2-4 mins (time 0 min). During the OGTT further blood samples will be taken at 15, 30, 60, and 120 minutes. The blood at each time point will be placed into a fluoride oxalate tube (1ml) for plasma glucose and into a serum tube for analyses of insulin and c-peptide.

The insulin sensitivity index will be calculated from the OGTT according to four different equations: the

Matsuda-Index (IS_{OGTT}): $IS_{OGTT} = \frac{10000}{\sqrt{(glucose_0 * insulin_0) * (mean\ glucose * mean\ insulin)}}$,¹⁴ the HOMA-IR

(Homeostasis Model Assessment for Insulin Resistance): $HOMA - IR = \frac{FPG(\text{mmol/l}) * FSI(U/l)}{22.5}$ ¹⁵ and the

$QUICKI = \frac{1}{\log(insulin_0) + \log(glucose_0)}$ ¹⁶. The last equation was proposed by Stumvoll et al. (insulin

sensitivity index ISI): $ISI = 0.222 - 0.00333 * BMI - 0.0000779 * Ins_{120} - 0.000422 * age$ ¹⁷.

Beta-cell function will be estimated in the fasting state with $HOMA - \beta = \frac{20 * Insulin_0}{Glucose_0 - 3.5}$ ¹⁵ and during

the OGTT with the Stumvoll-Index: $1st\ phase = 1283 + 1.829 * Ins_{30} - 138.7 * Glc_{30} + 3.772 * Ins_0$ plus $2nd\ phase = 286 + 0.416 * Ins_{30} - 25.94 * Gluc_{30} + 0.926 * Ins_0$ ¹⁷ and the ratio

of the incremental insulin to glucose response over the first 30min during the OGTT $\frac{\Delta Insulin(30)}{\Delta Glucose(30)}$.

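### Section 12.10 lets REE, a cohort primary outcome, be measured after 3 h without food, while under table 11.1 only the ADF group must arrive overnight-fasted, so the REE contrast may be confounded by prandial state

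*Protocol*

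**What the plan says.** Protocol section 8.1 lists "Differences in resting energy expenditure between groups" among the cohort primary outcomes. Table 11.1 and the visit list in 11.2 both place the REE measurement at Visit 2, for both groups.

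Section 12.10 sets the conditions for REE: a rest period, 8 hours or more of sleep, and measurement "after at least 3 hour fasting". This rule is the same for both groups and is a minimum.

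Section 12.1 is stricter for the glucose test: "The OGTT will be performed after an overnight fast (apart from water").

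The two descriptions of Visit 2 differ on who has that test. In table 11.1 the OGTT entry for Visit 2 reads "X (ADF group only"). In section 11.2 the Visit 2 list contains "Oral glucose tolerance test (OGTT") with no group restriction. The visit list mentions fasting only at Visit 1 ("Baseline blood tests (fasting")); the Visit 2 blood-sampling item does not.

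For the pilot RCT, table 11.3 gives both OGTT and REE at Visit 4 to all participants.

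**The concern.** On a day when both groups have REE measured, table 11.1 binds one group to an overnight fast through its OGTT. The other group is held only to the 3 h rule in 12.10. The fasting state required at the REE measurement then depends on group membership. If energy expenditure is still raised 3 h after a meal, whatever remains of that rise in fed controls enters the group difference.

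The cohort comparison is not randomised, and a larger sample would not remove the problem. The visit passages do not ask for time since last intake to be recorded, so the effect could not be separated out afterwards. If REE is taken before the glucose load, fed controls would make ADF appear to lower REE. That is a plausible-looking result, and it would be hard to recognise as an artefact.

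**Working it through.** **Step 1: required fasting state at Visit 2 REE, under each reading.**

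| Reading | ADF group | Controls |
|---|---|---|
| Table 11.1 governs | overnight (OGTT, 12.1) | at least 3 h (12.10) |
| Section 11.2 governs | overnight (OGTT, 12.1) | overnight (OGTT, 12.1) |

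The asymmetry exists under the first reading only. The sleep condition in 12.10 points to a morning measurement but does not exclude breakfast.

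**Step 2: order of REE and OGTT.** REE comes before the OGTT in the 11.2 list, but the list is not stated to be a sequence. REE taken first would find ADF participants overnight-fasted. REE taken after the 75 g glucose drink would not, although the 3 h minimum would still apply to them if the drink counts as ending the fast.

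**Step 3: size.** The protocol has no figure to reproduce here: it gives neither an REE standard deviation nor a meal effect. What follows is an illustration.

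- From the protocol: 30 ADF and 60 control subjects (section 4; section 10.1 still gives 50 and 50), and a 5% significance level (section 12.26), taken as two-sided and before the planned multiplicity correction.
- Assumed: residual post-meal rise f = 3-8% of REE in a fed control; between-person SD = 12-15% of mean REE; share s of controls fed about 3 h earlier; no ADF participant fed; no true difference. The extra spread from mixing fed and fasted controls is ignored.

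Spurious shift in SD units: b = f × s / SD.
Standard error in SD units: √(1/30 + 1/60) = 0.2236.
Noncentrality: b / 0.2236. Rejection probability from the noncentral t with 88 degrees of freedom, with the normal approximation alongside.

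| Share fed | b, smallest | b, largest | False positives, noncentral t | Normal approximation |
|---|---|---|---|---|
| 0 | 0 | 0 | 5% | 5% |
| 1/4 | 3 × 0.25 / 15 = 0.05 | 8 × 0.25 / 12 = 0.17 | 5.6-11.4% | 5.6-11.6% |
| 1/2 | 3 × 0.5 / 15 = 0.10 | 8 × 0.5 / 12 = 0.33 | 7.3-31.4% | 7.3-32.0% |
| 1 | 3 / 15 = 0.20 | 8 / 12 = 0.67 | 14.3-83.9% | 14.5-84.7% |

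The share of controls who have eaten matters as much as the assumed meal effect, and the protocol leaves that share open.

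**Step 4: the RCT.** Both arms come from the controls, so their Visit 2 condition should be balanced by randomisation, and at Visit 4 all have the OGTT. No between-arm bias follows. Within a person, Visit 2 REE could be at 3 h and Visit 4 REE overnight-fasted. That shift adds noise to the change and could appear as a fall in REE in the paired within-group comparisons planned in section 12.26.

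**The case against.** The 3 h rule is a minimum and is identical for both groups. Nothing says that controls eat before Visit 2, and after 8 hours of sleep many may simply arrive fasted. Section 11.2 lists the OGTT at Visit 2 without restriction, although the same list does mark another item as meant for controls only. On that reading everyone fasts overnight and the problem vanishes. Attendance instructions may also stand in participant information that is not among the pages available. Finally, section 12.26 calls the analyses descriptive and exploratory and plans a multiplicity correction, so a nominal 5% test overstates the formal consequence.

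Much of this stands. A reader might infer that the REE difference is biased, or that the protocol will make ADF seem to lower REE. The documents support neither statement. They permit a group-linked difference in fasting state but do not require one, and with no fixed order of REE and OGTT the direction is uncertain. Nor can the 14-84% range be quoted alone, because it assumes that every control is measured at about 3 h. The honest lower end is 5%, meaning no effect.

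The objection does not remove the defect. Table 11.1 is the only place that says expressly which group has the Visit 2 OGTT, and it restricts the test to ADF. As long as 11.1 and 11.2 disagree, site staff cannot tell from the protocol whether controls must fast, and 12.10 does not settle it. An exploratory analysis is distorted by a confounded measurement just as a confirmatory one is.

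**Conclusion.** The concern holds as a risk of confounding. The protocol sets no common fasting state for REE beyond 3 h. If table 11.1 governs, only the ADF group is bound to an overnight fast on the day a primary outcome is measured. If section 11.2 governs, this asymmetry does not arise.

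The size cannot be derived from the protocol. Under the stated assumptions the unadjusted false-positive rate runs from 5% with no controls fed, through about 6-12% with a quarter fed, to about 14-84% with all measured at 3 h. An apparent lowering of REE by ADF is the expected direction only if REE precedes the glucose load. In the RCT the consequence is limited to a possible shift between Visits 2 and 4 within a person.

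The change is worth making: it concerns a primary outcome in an unrandomised comparison, and the remedy costs very little.

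**What to change.** In section 12.10, replace the 3 h minimum with the overnight fast already defined in 12.1, for all participants at Visits 2 and 4. State that REE is measured before any glucose load. Record hours since last intake and whether the previous day was a fast or a feed day: a common overnight minimum does not by itself equalise time since last intake in people who fast on alternate days.

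Reconcile table 11.1 with section 11.2 on who has the OGTT at Visit 2. The REE condition should not depend on how that is settled.

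Cost: a sentence or two in 12.10, two recorded items, and one correction to the schedule. Controls would have to attend Visit 2 fasted, which is a small inconvenience. No procedure is added.
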